## SCHEMA

TNBC – triple negative breast cancer; CNS – central nervous system; SRS – stereotactic radiation to brain metastasis;

- \*D1 of Atezolizumab (A) will be administered 2-7 days before the initiation of SRS.
- Bx1 – Baseline tumor biopsy will be obtained within 28 days of starting Atezolizumab.
- Bx2 – Reassessment biopsy will be obtained between C2D1-C2D21.
- Imaging will be performed at screening within 4 weeks before starting Atezolizumab. Tumor assessments, including brain magnetic resonance imaging and computed tomography of the chest, abdomen and pelvis, will be performed every 6 weeks ( $\pm 1$  week) for the first 24 weeks on treatment, and every 9 weeks ( $\pm 1$  week) thereafter, with additional scans as clinically indicated.
- **Blood samples will be collected within 7 days before starting treatment (baseline), at day 1 ( $\pm 3$  days) of cycle #3, #5, #9, and at progression or off protocol therapy, whichever comes first.**
- **Cerebrospinal fluid collection will be performed at 3 times points (baseline, before cycle 3, and at progression or off protocol therapy, whichever comes first).**

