### 3.1 Eligibility Criteria

- 3.1.1 Participants must have histologically or cytologically confirmed Stage IV invasive breast cancer. Participants without pathologic or cytologic confirmation of metastatic disease should have unequivocal evidence of metastasis from physical examination or radiologic evaluation.
- 3.1.2 Either the primary tumor and/or metastatic tumor must be triple-negative as defined below:
- Hormone receptor status: the invasive tumor must be ER- and PR-negative, or staining present in <1% by immunohistochemistry (IHC)
  - HER2 status: the invasive tumor must be Human Epidermal Growth Factor Receptor 2 Negative (HER2-negative) by the ASCO CAP guidelines
- Note:** In cases where both primary tumor and metastatic sample(s) have been tested for ER, PR, and HER2, the triple-negative status of the most recent sample should be used.
- 3.1.3 Participants must have a diagnosis of brain metastases for which stereotactic radiation is indicated, as determined by a radiation oncologist.
- 3.1.4 The contrast-enhancing intraparenchymal brain metastases(s) must be well circumscribed and must have a maximum diameter of  $\leq 3.0$  cm in any direction on the enhanced scan.
- 3.1.5 Participants must not have more than 5 new or progressive lesions in the brain requiring stereotactic radiation treatment (greater than 5 total brain lesions are allowed as long as no more than 5 lesions require stereotactic radiation treatment).
- 3.1.6 Participants must have measurable extracranial disease as defined by RECIST 1.1.
- 3.1.7 Participants must be willing to undergo a research biopsy at baseline and at Cycle 2 Day 1 if extracranial metastases are safely accessible. Participants for whom biopsies cannot be safely performed must be willing to submit an archival primary and/or metastatic specimen. The biopsies may be waived with prior PI approval for the first 6 participants enrolled to the safety run in phase.
- 3.1.8 Prior systemic therapy:
- Participants must have discontinued systemic therapy at least 14 days prior to initiating protocol therapy.
  - There is no limit to the number of prior lines of systemic therapy. Participants who have not received any systemic therapy for metastatic disease are also eligible.
  - Participants may initiate or continue bisphosphonate therapy on study.

- 3.1.9 Prior local therapy:

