#### Prohibited Concomitant Medications

Subjects are prohibited from receiving the following therapies during the Screening and Treatment Phase of this trial:

- Antineoplastic systemic chemotherapy or biological therapy
- Immunotherapy not specified in this protocol
- Investigational agents other than atezolizumab
- Radiation therapy not specified in this protocol
- Any systemically active oral, injected, or implanted hormonal method of contraception except for progesterone coated intrauterine devices (IUDs) that had been previously implanted.
- Estrogen replacement therapy.
- Live vaccines within 28 days prior to the first dose of trial treatment and while participating in the trial. Examples of live vaccines include, but are not limited to, the following: measles, mumps, rubella, varicella/zoster, yellow fever, rabies, BCG, and typhoid vaccine.
- Systemic glucocorticoids should be avoided for any purpose other than to modulate symptoms from radiation, an event of clinical interest of suspected immunologic etiology, or emergent symptoms from brain metastasis. If corticosteroids are required for this purpose, the minimum effective dose should be used.
- Subjects may receive other medications that the investigator deems to be medically necessary.

There are no prohibited therapies during the Post-Treatment Follow-up Phase.

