## 10. STUDY CALENDAR

Screening evaluations are to be conducted within 28 days prior to initiating protocol therapy unless otherwise specified. Screening assessments occurring within 1 week prior to initiating study treatment do not need to be repeated on Cycle 1 Day 1.

Screening laboratory assessments must be done within 8 days prior to initiating protocol therapy. For women of childbearing potential, as defined in the eligibility criteria, a pregnancy test must be completed within 8 days prior to initiating protocol therapy. If a urine pregnancy test is positive or cannot be confirmed as negative, a serum pregnancy test will be required.

If the participant’s condition is deteriorating, laboratory evaluations should be repeated within 48 hours prior to initiation of the next cycle of therapy.

Assessments must be performed prior to administration of any study agent. Study assessments and agents should be administered within  $\pm$  3 days of the protocol-specified date, unless otherwise noted.

Day	Screening	Cycle 1			Cycle 2		Cycle 3	Cycle 4+		Cycle 5	Cycle 6		Off-Treatment g	Follow-Up
	Day -28 to day -1	Day 1	RT Day 1	10 days after RT	Day 1	Day 15-21	Day 1	Day 1	Day 15-21	Day 1	Day 1	Day 15-21		
Informed consent	X													
SRS Planning Appointment h	X													
Medical history b	X													
Physical exam c	X	X			X		X	X		X	X		X	
Radiation Oncologist Visit d			X d	X d										
Adverse event evaluation	X	X			X		X	X		X	X		X	
Vital signs e	X	X			X		X	X		X	X		X	
Weight	X	X			X		X	X		X	X			
Concurrent medications f	X	X			X		X						X	
ECOG Performance status	X	X			X		X	X		X	X		X	
Neurological Assessment	X	X			X		X						X	
Brain MRI e	X					X			X			X	X	X
CAP CT and/or MRI h	X					X			X			X	X	X
Hematology panel i	X	X			X		X						X	
Chemistry panel j	X	X			X		X						X	
TSH k	X	X			X		X	X		X	X			
Pregnancy test l	X													
Research Blood - cfDNA m		X	X				X	X m		X m	X m		X	X

Research Blood - Immune Markers a	X	X	X				X	X n		X n	X n		X	
Research Biopsy o	X				X								X	
Cerebrospinal Fluid Collection p	X					X							X	
Questionnaire q		X					X	X		X	X		X	X
General Impression Worksheet t	X				X		X	X		X	X			
Archival Tissue Collection	X													

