Atezolizumab		X			X		X	X		X	X			
Post RT Follow-up Visit u											X u			
Survival Status r														X

**Atezolizumab: 1200mg given IV q3 weeks on Day 1 of each cycle + Stereotactic Radiation: radiation will start 2-7 days after the first dose of atezolizumab**

- a. Stereotactic radiation planning appointment must occur at least 7 days prior to initiating radiation
- b. Medical history includes clinically significant disease, surgeries, and cancer history (including prior cancer therapies and procedures).
- c. A complete physical examination, including neurological examination, will be performed at screening. A limited physical exam, to include a neurological exam, will be performed at subsequent Day 1 visits.
- d. Participants will be seen by a radiation oncologist on day 1 of stereotactic radiation and 10 days after radiation completion (+/- 4 days).
- e. Vital signs to include: heart rate, systolic and diastolic blood pressures while the patient is in a seated position, respiratory rate, and temperature.
- f. Selected medications of interest received within 28 days before the first dose of trial treatment and 30 days after the last dose of trial treatment, including dosage, frequency, route, and dates of administration will be documented
- g. T-1 weighted perfusion MRI will be used. Screening MRI must be done within 14 days of the radiation initiation. Subsequent assessments should be done during the last 15-21 days of a cycle, q6weeks for the first 24 weeks (i.e. C2, 4, 6, 8) and then can be reduced to q9 weeks (i.e. C11, 14, 17, etc). If progression is suspected, an unscheduled assessment is permitted. An objective response (CR, PR) should be confirmed by repeat assessments 4-6 weeks after initial finding. Patients with CNS PD are allowed to continue on study for 4-6 weeks to confirm PD on MRI. For those taken off-study for reasons other than progressive disease in the CNS, assessments should continue to be repeated every 6-12 weeks until progression or beginning a new cancer therapy regimen. It is understood that it may not always be feasible for patients to return for restaging evaluation after coming off protocol therapy; however, it is strongly encouraged. Failure to complete CNS restaging after a patient has been taken off protocol therapy will not constitute a protocol violation.

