  - c) *Definition of new lesion(s):* The finding of a new CNS lesion should be unequivocal and not due to technique or slice variation. A new lesion is one that was not present on prior scans. If the MRI is obtained with  $\leq 1.5$  mm slice thickness, then the new lesion should also be visible in axial, coronal, and sagittal reconstructions of  $\leq 1.5$  mm projections. If a new lesion is equivocal, for example because of its small size (i.e.,  $\leq 5$  mm), continued therapy may be considered, and follow up evaluation will clarify if it represents truly new disease. If repeat scans confirm there is definitely a new lesion, then progression should be declared using the date of the initial scan showing the new lesion. In the case of immunotherapy, new lesions alone may not constitute progressive disease (see “Guidance in the case of new lesion(s) while on immunotherapy” below).
  - d) *Definition of Unequivocal Progression of Non-Target Lesion(s):* When the patient also has measurable disease, to achieve ‘unequivocal progression’ on the basis of non-target disease alone, there must be an overall level of substantial worsening in non-target disease such that, even in the presence of SD or PR in target disease, the overall tumor burden has increased sufficiently to merit discontinuation of therapy. When the patient has only non-measurable disease, there must be an overall level of substantial worsening to merit discontinuation of therapy.

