### 11.2.3 Methods for Evaluation of Disease

All measurements should be taken and recorded in metric notation using a ruler, calipers, or a digital measurement tool. All baseline evaluations should be performed as closely as possible to the beginning of treatment and never more than 4 weeks before the beginning of the treatment.

The same method of assessment and the same technique should be used to characterize each identified and reported lesion at baseline and during follow-up. Imaging-based evaluation is preferred to evaluation by clinical examination unless the lesion(s) being followed cannot be imaged but are assessable by clinical exam.

Clinical lesions. Clinical lesions will only be considered measurable when they are superficial (*e.g.*, skin nodules and palpable lymph nodes) and  $\geq 10$  mm in diameter as assessed using calipers (*e.g.*, skin nodules). In the case of skin lesions, documentation by color photography, including a ruler to estimate the size of the lesion, is recommended.

Chest x-ray. Lesions on chest x-ray are acceptable as measurable lesions when they are clearly defined and surrounded by aerated lung; however, CT is preferable.

Conventional CT and MRI. This guideline has defined measurability of lesions on CT scan based on the assumption that CT thickness is 5mm or less. If CT scans have slice thickness greater than 5 mm, the minimum size of a measurable lesion should be twice the slice thickness. MRI is also acceptable in certain situations (*e.g.* for body scans).

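### The baseline CT may be taken while prior systemic therapy is still running, so shrinkage from that therapy can count as extracranial RECIST or abscopal response

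*Combined protocol and SAP*

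**What the plan says.** **Baseline window.** The schema reads "Imaging will be performed at screening within 4 weeks before starting Atezolizumab". Section 11.2.3 asks for baseline evaluations "performed as closely as possible to the beginning of treatment and never more than 4 weeks before the beginning of the treatment". Section 10 reads "Screening evaluations are to be conducted within 28 days prior to initiating protocol therapy unless otherwise specified", and its screening column runs from day -28 to day -1. Calendar footnote h, on the body CT, adds nothing on the order of the scan and the last prior treatment.

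**Prior therapy.** Section 3.1.8 reads "Participants must have discontinued systemic therapy at least 14 days prior to initiating protocol therapy". Section 5.3.1 reads "Subjects are prohibited from receiving the following therapies during the Screening and Treatment Phase of this trial", and its list includes antineoplastic systemic chemotherapy and biological therapy.

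**Endpoints that use the baseline.** RECIST partial response is a fall of at least 30% from the baseline sum of diameters (11.2.3.1). Abscopal response is a fall of at least 30% from baseline in any measurable non-irradiated lesion, with the best-responding lesion reported (11.4.3). Extracranial ORR is a key secondary endpoint, tested against 10% by an exact binomial test (13.6.1). Abscopal response is exploratory (1.4.5).

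**The concern.** Patients enter because brain lesions need radiation (3.1.3, 3.1.5). Outside the brain they need only measurable disease (3.1.6), and no criterion asks for extracranial progression on the last therapy. A patient whose brain disease progresses while extracranial disease is shrinking on that therapy is therefore eligible.

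If that patient's CT is taken on day -28 and treatment continues to day -14, any shrinkage in between is measured from the trial baseline and belongs, on paper, to the trial regimen. There is no control arm in which the same carry-over would appear. Section 13.6.1 uses extracranial response to look for a signal of an abscopal effect, which is the pattern that carry-over would imitate.

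The opposite error is also possible. Growth between the CT and the first dose makes response harder to reach. It also counts toward extracranial progression, because progression is judged against the smallest sum including baseline, while the PFS clock starts at the first dose.

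**Working it through.** **1. Day arithmetic (first dose as reference).**
- Permitted CT: day -28 to day -1 (schema, 10, 11.2.3).
- Prior systemic therapy permitted until day -14 (3.1.8).
- A CT on days -28 to -15 can therefore predate the last permitted prior dose. That is 14 of the 28 permitted days.
- If Screening means the calendar's day -28 to day -1, Section 5.3.1 forbids on days -28 to -15 what 3.1.8 allows.
- The largest gap from CT to first dose is 28 days: 28 / 30.4375 = 0.92 months, or 46% of the 2-month null median PFS in Section 13.2.

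**2. The plan's own ORR figure.** Inputs from 13.6.1: N = 45, null 10%, alternative 25%, one-sided error at most 0.05.
- P(X ≥ 8 | 45, 0.10) = 7.6%, too large.
- P(X ≥ 9 | 45, 0.10) = 3.2%, so the rule is 9 or more responders.
- P(X ≥ 9 | 45, 0.25) = 82.7%, against 82% stated. The plan's figure reproduces.

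**3. Illustration of carry-over.** The documents give neither the number of patients scanned on prior therapy (k) nor the resulting rise in response probability (r). Both are assumptions. With a true regimen response rate of 10%, the responder count is the sum of Binomial(45 - k, 0.10) and Binomial(k, 0.10 + r). The false-positive rate is P(sum ≥ 9):

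| Exposed, k | r = 5 points | r = 10 points | r = 20 points |
|---|---|---|---|
| 0 | 3.2% | 3.2% | 3.2% |
| 4 of 45 | 4.1% | 5.0% | 7.3% |
| 9 of 45 | 5.3% | 8.2% | 16.4% |

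The expected number of extra responders is k × r. For k = 9 and r = 10 points it is 9 × 0.10 = 0.9, so less than one spurious response on average takes the error from 3.2% to 8.2%. The table models upward bias only; growth before dose 1 is not in it.

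**The case against.** **The ban in 5.3.1 may close the gap.** If it governs from day -28, a screening CT is already off chemotherapy and biological therapy. This would be a good answer if the documents said so. As written, 3.1.8 permits what 5.3.1 forbids, and a site cannot tell which applies. The instruction in 11.2.3 to image close to treatment start sets no order between scan and last dose.

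**Exposure may be small.** Section 2.4 says these patients often progress outside the brain as well, and 3.1.8 admits patients with no prior therapy for metastatic disease. The first on-study scan falls on Cycle 2 Day 15 to 21, about seven weeks or more after a last prior dose on day -14, and shrinkage must still be visible then. The 20-point column gives exposed patients a 30% response probability under the null, above the regimen's own 25% alternative. All of this stands. It limits the likely size but does not remove the gap.

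**The brain reading.** A reader might infer that the schema's 4 weeks also permits a brain MRI up to 28 + 7 = 35 days before radiation, so that untreated growth or lesions first seen at planning enter the primary PFS. The documents do not support this. The calendar's 28 days yield to specific rules, and footnote g is one: "Screening MRI must be done within 14 days of the radiation initiation". The radiation timing and planning subsections (5.2.4.1.1, 5.2.4.1.5) repeat that limit. With radiation 2 to 7 days after dose 1, the earliest compliant MRI is day 2 - 14 = -12 to day 7 - 14 = -7, after the last permitted prior dose. An MRI that meets this rule also meets the schema. Under 11.1.1.5, "A new lesion is one that was not present on prior scans", so a lesion on the planning MRI is not new later. CNS target progression also needs a 5 mm increase in at least one lesion as well as 20% (11.1.1.4). What remains for the brain is a missing cross-reference in the schema.

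**Conclusion.** The point holds for extracranial disease only. A compliant baseline CT can predate the last dose of prior therapy, no provision prevents it, and the two sections on prior therapy contradict each other for days -28 to -15.

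A reader might go further and infer that the ORR test is anti-conservative. The documents do not show that. The error rates of 4.1% to 16.4% rest on assumed exposure and carry-over, and growth before dose 1 pulls the other way on both response and PFS. Neither the net size nor the net direction can be derived.

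No stated sample size or power is wrong, since the imaging window is not an input to either. Severity is minor to moderate: a key secondary and an exploratory endpoint are exposed, in a single-arm setting where a small number of misattributed responses can matter.

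**What to change.** 1. In the schema, Section 11.2.3 and calendar footnote h, state that the RECIST and abscopal baseline CT is taken after the last dose of prior systemic therapy and within 4 weeks of Cycle 1 Day 1. The interval already required by 3.1.8 leaves at least 14 days for this. Cost: later scheduling, or a repeat CT in the few patients already scanned on prior therapy.
2. Pre-specify a sensitivity analysis of ORR and abscopal response that leaves out patients whose baseline CT predates their last prior dose. Cost: a slightly smaller N in that analysis, and recording the date of the last prior dose beside the CT date.
3. Reconcile 3.1.8 with 5.3.1, so that it is clear which rule on prior therapy applies during Screening. Cost: wording only.
4. In the schema, cross-refer to the existing 14-day brain MRI rule. Cost: wording only.

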## **1. OBJECTIVES**

### **1.1 Study Design**

- 1.1.1 This is an open-label, single arm phase II study assessing progression-free survival (PFS) in patients with triple-negative breast cancer (TNBC) and brain metastases who will receive stereotactic radiation in combination with atezolizumab. Atezolizumab will be administered at 1200mg IV every 3 weeks until disease progression in either CNS or extra-CNS site(s) according to RANO-BM and RECIST criteria, respectively. The first dose of Atezolizumab should be administered 2-7 days prior to starting radiation. Research biopsies will be performed at baseline (mandatory if there is accessible extracranial metastasis) and at Cycle 2 Day 1. An optional research biopsy will be collected at time of progression if a participant has achieved a prolonged response defined as complete or partial response or stable disease for  $\geq 24$  weeks).

### **1.2 Primary Objectives**

- 1.2.1 To evaluate the efficacy of atezolizumab in combination with stereotactic radiation, as defined by bi-compartmental PFS according to RANO-BM criteria, in patients with TNBC and brain metastases.

### **1.3 Key secondary objectives**

- 1.3.1 To evaluate the extracranial objective response rate (ORR) by RECIST 1.1 criteria among patients with TNBC and brain metastasis treated with atezolizumab in combination with stereotactic radiation [Eisenhauer *et al.*, 2009].
- 1.3.2 To evaluate overall survival (OS) of patients with TNBC and brain metastasis treated with atezolizumab in combination with stereotactic radiation.

### **1.4 Exploratory Objectives**

#### Exploratory safety objectives

- 1.4.1 To evaluate the short term, 6-month, and 12-month safety and tolerability of atezolizumab in combination with stereotactic radiation in patients with TNBC and brain metastases.

### Exploratory efficacy objectives

- 1.4.2 To evaluate the central nervous system (CNS) response rates according to response assessment in neuro-oncology-brain metastases (RANO-BM) criteria [Lin *et al.*, 2015] (Section 11.1.1).
- 1.4.3 To evaluate the CNS response rates according to response assessment in immunotherapy neuro-oncology-brain metastases (iRANO-BM) criteria [Okada *et al.*, 2015].
- 1.4.4 To evaluate the extracranial ORR according to immune-related response criteria (irRC) [Wolchok *et al.*, 2009].
- 1.4.5 To evaluate the abscopal response rate (ARR), according to abscopal response definition [Golden *et al.*, 2015] (Section 11.4.3).
- 1.4.6 To evaluate the proportion of participants with stable or responsive disease in both CNS and non-CNS at 16 and 24 weeks.
- 1.4.7 To evaluate PFS according to the RECIST 1.1 single-compartmental model.
- 1.4.8 To evaluate PFS according to the RANO-BM criteria.
- 1.4.9 To describe the site of first progression (CNS vs extracranial vs both)
- 1.4.10 To describe the type of CNS progression (new lesion(s), progression of non-target lesions, progression of target lesions, progression of stereotactic radiation-treated lesions, radiation necrosis in stereotactic radiation-treated lesions, or a combination of these)
- 1.4.11 To describe the type of extracranial progression (new lesion(s), progression of non-target lesions, progression of target lesions, or a combination of these)

### Exploratory patient-reported outcome objectives

- 1.4.12 To evaluate the impact of treatment with atezolizumab and stereotactic radiation in patients with TNBC and brain metastases on PROs, as measured by the M.D. Anderson Symptom Inventory-Brain Tumor (MDASI-BT) assessment
- 1.4.13 To evaluate the relationship of CNS ORRs according to the RANO-BM criteria with PRO endpoints, as measured by the MDASI-BT
- 1.4.14 To evaluate the relationship of CNS ORRs according to the iRANO criteria with PRO endpoints, as measured by the MDASI-BT
- 1.4.15 To evaluate the impact of the study treatment, for these same patients, on general health status assessed by EQ-5D questionnaire.

